4.0 RISK AND BENEFIT ANALYSIS

There are potential risks associated with transcatheter heart valve implantation. There are risks related to the overall procedures (complications associated with standard cardiac catheterization which include bleeding, infection, stroke, death, cardiac arrest, pacemaker implantation, allergic reactions, emergency open heart surgery, and emergency blood transfusion, prolonged hospital stay, renal failure, groin lymphocele, limb ischemia, myocardial infarction, injury to adjacent structures including nerves, blood vessels, or other structures.) In addition, there are also risks associated with the valve itself which include valve embolization and/or migration and the emergent need for open heart surgery and possibly death, as well as valve thrombosis which can lead to death, stroke, pulmonary embolism, or venous thrombosis. Structural valve deterioration may also occur in the form of wear, fracture, calcification, leaflet tear/tearing from the stent posts, leaflet retraction, suture line disruption of components of a prosthetic valve, thickening, stenosis.

There are risks associated with stenting of the IVC for valve implantation. These include migration of the stent and injury to the vessels of the heart or the heart itself, as well as venous thrombosis and stroke. Although these risks are present, the potential of a new therapy which improves the quality of life in those patients who are otherwise ineligible for surgery outweighs these potential risks.

Pleural effusions may occur either immediately post-operatively, or at follow up. It is recommended that a trial of diuretic therapy, as well as attempts at diagnosis of the effusion (exudative vs. transudative) be attempted if the patient becomes symptomatic. If diuretic therapy fails, a thoracentesis should be considered for symptomatic relief. If the effusion reoccurs, additional thoracenteses may be considered. Alternatively, the placement of a permanent drainage catheter, or pleuredesis may be another option in patients with continued fluid accumulation who remain symptomatic.

4.1 Efforts to minimize procedure risks

Efforts to minimize procedural risks will be addressed in the following manner.

4.1.1. Site Heart Team and Executive Committee Presentation

All possible patients will be presented at a site heart team conference. There the data will be reviewed, including any aspects which may or may not affect the possible success of the procedure. After this step, patients will be presented to a panel of experienced operators outside of the local heart team institution, the executive committee. There, the data will be reviewed a second time prior to enrollment in the trial.

4.1.2. Data Safety Monitoring Board (DSMB)

A DMSB will be established. The DSMB is independent from the Sponsor, the investigators, or anyone involved in the medical care of the study subjects. Members will not have scientific, financial, or other conflict of interest related to the Sponsor or the investigators. The committee will be selected by the overall Principal Investigator and managed independently.

The members must have the following characteristics:

- working professionally as physicians or statisticians;
- at least one member with specific expertise in cardiothoracic surgery clinical trials;
- no relevant conflicts of interest;
- they will not be involved in the conduct of this trial in any other capacity, such as principal investigators, sub-principal investigators;
- they will not be engaged in any simultaneously occurring competitive trials;
- they should not be on the NIDPOE or debarred list of investigators.

Members will not serve on the DSMB, Clinical Event Adjudication Committee (CEC) or Operating Committee of a competing device trial. Members will not have any affiliation with the core laboratories, the data coordinating center, or the principal investigator of the trial. The DSMB committee will review all safety data from the HOVER Trial and make recommendations based upon the safety analyses. The frequency of the DSMB meetings will be determined prior to study commencement; however, the DSMB may call a meeting at any time if there is reason to suspect safety is an issue. DSMB oversight for this trial is expected to be rigorous with frequent review of all essential safety data. The DSMB chairperson will notify the principal investigator of any safety or compliance issues. They will also provide confidential recommendations, when necessary, of study termination. All DSMB reports will remain strictly confidential, but will be made available to regulatory authorities. The principal investigator will notify the FDA if any member of the DSMB advises to terminate the study due to safety concerns.

4.1.3. Interim Monitoring and Stopping Rules

The interim monitoring and stopping rules will focus on the 6-month mortality. Based on current literature, it is reasonable to assume a 6-month mortality of at least 30% for the high risk patients targeted in this clinical trial ³¹. For the purpose of this trial, we will focus on device-related mortality.

The interim monitoring will be implemented with stopping rules when 3, 6, and 9 patients have been enrolled and treated with the protocol device. The proposed stopping rules are:

Number of patients on trial:	When number of 6-month deaths \geq :	Probability of stopping the trial early when the true 6-month mortality is 30%:
3	2	0.216
6	3	0.105
9	4	0.064
15	6	0.064

As it can be seen from the above table, the probability of stopping the trial early is very small ($\leq 10.5\%$) assuming the true 6-month mortality rate is no more than 30% when there are at least 6 patients

enrolled and treated on the clinical trial. When there are only 3 patients enrolled, we are only stopping the trial early when two (or more) out of the first three patients died within 6 months on trial due to a device-related death. This probability is reasonably small as well (21.6%).

In addition to mortality, should valve thrombosis occur in $\geq 30\%$ of patients at 6-months, the trial will be paused to evaluate if any additional precautions are required.

The trial PI ([name] [name], MD), working along with the study DSMB, will monitor other safety parameters such as significant surgery complications, one-year mortality, overall survival, and event-free survival at least biannually (every 6 months) as well in an effort to make certain that the patients on trial are not inadvertently harmed by the proposed protocol treatment.

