7.2 Serious Adverse Events

A serious adverse event (SAE) is any untoward medical occurrence that:

- results in death
- is life-threatening, i.e., an event that, in the view of the investigator, places the subject at immediate risk of death from the event as it occurred (it does not include an event that could have caused death if it had been more severe)
- requires inpatient hospitalization or prolongs the existing hospitalization
- results in persistent or significant disability or incapacity, where disability is defined as a substantial disruption of a person's ability to conduct normal life functions, either reported or defined as per clinical judgment
- is a congenital anomaly or birth defect (if exposure to product just before conception or during pregnancy resulted in an adverse outcome in the child)

All investigators will be responsible for reporting serious adverse events to the sponsor and their reviewing IRBs in accordance with local guidelines. In addition, all SAEs will be reviewed by an independent Data Safety Monitoring Board (DSMB) in accordance with their charter. (An SAE will be reported to the Sponsor and DSMB Chair within 24 hours from when the event was discovered and the SAE CRF will be submitted no later than ten (10) days after the SAE was discovered) Study device causality for SAE's will be graded as unlikely, possible or probably.

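### The mortality stopping boundaries are justified at a 30% death rate not limited by cause, but the rule is said to count device-related deaths, for which no reference rate is found

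*Combined protocol and SAP*

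**What the plan says.** Section 4.1.3 (Interim Monitoring and Stopping Rules) of the combined protocol and SAP first sets a background rate: "it is reasonable to assume a 6-month mortality of at least 30% for the high risk patients targeted in this clinical trial". The next sentence narrows the event: "For the purpose of this trial, we will focus on device-related mortality". The explanation of the first look repeats the restriction, describing two or more of the first three patients who "died within 6 months on trial due to a device-related death".

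On timing, the section says "The interim monitoring will be implemented with stopping rules when 3, 6, and 9 patients have been enrolled" and treated. The table has those three looks and a fourth row at 15 patients. Its boundaries are 2, 3, 4 and 6 deaths. Its last column, headed "Probability of stopping the trial early when the true 6-month mortality is 30" per cent, gives 0.216, 0.105, 0.064 and 0.064. The text calls the chance of stopping very small, at most 10.5%, "assuming the true 6-month mortality rate is no more than 30% when there are at least 6 patients", and reports the three-patient look separately as 21.6%.

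The column of boundaries refers to 6-month deaths without a cause. Section 2.3 (Statistical Analysis), which points to these rules, refers only to 6-month mortality.

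On attribution, section 7.2 says device causality for serious adverse events "will be graded as unlikely, possible or probably"; section 7.1 uses the same three grades. The Unanticipated Adverse Device Effect (UADE) form uses a different scale: not, possibly, probably or definitely related, or unknown. Appendix B, Table 2 (VARC-2 mortality) has its own categories of procedure-related and valve-related death.

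**The concern.** A stopping boundary is justified by how often it is crossed at a tolerable rate of the counted event and at an excessive one. Here the rate belongs to one event (death, with no cause stated) and the count, by the section's own words, to a narrower one. A DSMB member cannot tell from the table what device-related death rate the rule tolerates, or how often it would stop the trial if that rate were too high. Because the table heading and section 2.3 omit the restriction, two careful readers could also count different deaths. At a boundary of two in three, the classification of a single death can decide whether the trial stops.

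This is the trial's only numeric mortality boundary. Separately, the text relies on single-look probabilities and never gives the overall chance of stopping.

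**Working it through.** **Inputs.** From section 4.1.3: looks at n = 3, 6, 9 (and the table's 15), boundaries 2, 3, 4, 6, rate p = 0.30. Like the table, the calculation takes 6-month status as known for every patient counted at each look. The other values of p are assumptions.

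**Method.** Exact binomial recursion. At each look, add the deaths among the new patients, take out the paths that reach the boundary, and carry the rest forward.

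**Reproducing the table at p = 0.30.** Among three new patients, the probabilities of 0, 1, 2 and 3 deaths are 0.343, 0.441, 0.189 and 0.027, so P(≥2) = 0.189 + 0.027 = 0.216.

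- n = 3: 0.2160. Carried forward: 0.343 with no deaths, 0.441 with one.
- n = 6: 0.343 × 0.027 + 0.441 × 0.216 = 0.0093 + 0.0953 = 0.1045 (unrounded terms). Carried forward: 0.1176 with none, 0.3025 with one, 0.2593 with two.
- n = 9: 0.3025 × 0.027 + 0.2593 × 0.216 = 0.0082 + 0.0560 = 0.0642.
- n = 15: the same step with six new patients gives 0.0636.

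All four printed values are reproduced. They are first-crossing probabilities. The plain binomial tails at 30% would be 0.216, 0.256, 0.270 and 0.278, which match only the first row.

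**Cumulative probability at 30%.** First-crossing probabilities add:

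- n = 6 or n = 9: 0.1045 + 0.0642 = 0.1687, or 16.9%.
- By n = 9: 0.2160 + 0.1045 + 0.0642 = 0.3847, or 38.5%.
- By n = 15: 0.3847 + 0.0636 = 0.4483, or 44.8%.

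**Same boundaries at other rates of the counted event.**

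| Rate | n=3 | n=6 | n=9 | n=15 | By n=9 | By n=15 |
|---|---|---|---|---|---|---|
| 10% | 0.0280 | 0.0075 | 0.0026 | 0.0007 | 3.8% | 3.9% |
| 15% | 0.0607 | 0.0218 | 0.0099 | 0.0049 | 9.2% | 9.7% |
| 20% | 0.1040 | 0.0440 | 0.0236 | 0.0166 | 17.2% | 18.8% |
| 30% | 0.2160 | 0.1045 | 0.0642 | 0.0636 | 38.5% | 44.8% |
| 35% | 0.2817 | 0.1368 | 0.0844 | 0.0883 | 50.3% | 59.1% |
| 40% | 0.3520 | 0.1659 | 0.0995 | 0.1038 | 61.7% | 72.1% |

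Each per-look value rises with the rate up to 30% (checked in steps of one percentage point). The printed values are therefore upper bounds for any lower rate.

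**As a share of total mortality.** If total 6-month mortality were exactly 30% and half of it were device-related, the rate would be 0.5 × 30% = 15% and the chance of crossing by n = 9 would be 9.2%, against 38.5% if every death counted.

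The 15-patient row falls at full enrolment, so a crossing there cannot stop accrual. The n = 9 column is the relevant one for early stopping.

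**The case against.** The strongest reply is that the table does what it sets out to do. It claims that stopping is unlikely when mortality is no more than 30%. Device-related deaths cannot exceed all deaths, so if their rate is below 30% the claim holds with room to spare. A rule that counts fewer events will cross less often, and that may be wanted where background mortality is high. This stands as a defence of the false-stopping claim. It does not supply the other half of a safety rule, its behaviour at an excessive rate.

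A reader might infer that the 10.5% statement is false. It is not: it is tied to looks with at least six patients, and at 30% those per-look values are as printed, whichever deaths are counted. It misleads only if taken as the overall chance of stopping, or applied above 30%. Because the entries are first-crossing probabilities, a reader who knows that can add them.

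A reader might also infer a contradiction between a reference of at least 30% and a bound of no more than 30%. The second is an ordinary one-sided bound evaluated at its worst case, and it can fit device-related deaths. But the cited literature rate is then not their reference rate.

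Could 30% itself be the tolerated device-related rate? The section presents it as the expected mortality of the target patients and nowhere calls it a device-related limit.

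Oversight beyond the table is substantial. Section 7.2 says "all SAEs will be reviewed by an independent Data Safety Monitoring Board (DSMB) in accordance with their charter". Section 4.1.2 lets the DSMB meet at any time. Section 4.1.3 provides for survival review at least every six months and a pause if valve thrombosis reaches 30%. Section 2.3 allows immediate suspension of accrual. This limits the consequence but does not make the boundary interpretable.

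**Conclusion.** The point stands as a mismatch between the event counted and the rate used to justify the count, with inconsistent wording about which deaths count. At assumed device-related rates of 10% to 20%, the chance of crossing by the ninth patient is 3.8% to 17.2%, against 38.5% at 30%. Whether those figures are acceptable depends on a reference rate that the available text does not give.

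Two stronger readings are tempting and unsupported. One is that the table is miscalculated; it reproduces exactly. The other is that the rule is unsafe or too weak. That cannot be concluded without a stated device-related rate, and the rates used here are assumptions.

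The absence of a reference rate is established only for the text available. The end of section 1.0 (Background) and the DSMB charter were not available, and either might contain one or define attribution. The event mismatch does not depend on them, because it lies within section 4.1.3. The issue should be fixed, but it does not invalidate the trial.

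**What to change.** State in section 2.3, in section 4.1.3 and in the table heading which deaths count, and reconcile the reference rate with that event.

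- **If device-related deaths are kept:** state the device-related 6-month death rate judged acceptable, check the boundaries against it, and report per-look and cumulative crossing probabilities at that rate and at higher rates. Define device-related consistently across the causality scale in sections 7.1 and 7.2, the UADE form and the VARC-2 death categories in Appendix B.
- **If all-cause deaths are intended:** remove the device-related wording and label the column as the per-look first-crossing probability. Add the cumulative values: 38.5% by n = 9 and 44.8% by n = 15 at 30%; 50.3% and 59.1% at 35%. Limit the statement that stopping is very unlikely to per-look values at a rate of no more than 30%.

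Any new boundaries are for the sponsor and the DSMB to choose; none is proposed here.

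The cost is protocol wording and one recomputed table, with no new patients, visits or data. The stated probabilities may look less favourable, and with at most 15 patients any boundary separates rates only coarsely.

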IMA or other critical conduit(s) crossing midline and/or adherent to posterior table of sternum	A patent IMA graft that is adherent to the sternum such that injuring it during reoperation is likely. A patient may be considered at extreme risk if any of the following are present: The conduit(s) are radiographically indistinguishable from the posterior table of the sternum. The conduit(s) are radiographically distinguishable from the posterior table of the sternum but lie within 2–3 mm of the posterior table.	Axial CT scan images illustrating the graft crossing the midline so that the distance from sternum to graft can be measured. Angiogram from the lateral and PA projections and/or a CPR or VR (volume rendering) 3D reconstructed CT scan image showing relationships between the graft and the sternum
Severe pulmonary hypertension Severe right ventricular dysfunction	Primary or secondary pulmonary hypertension with PA systolic pressures greater than two-thirds of systemic pressure Criteria as defined by the guidelines (eg, TAPSE <15 mm, RV end-systolic area >20 cm ² , etc)†	Echocardiography, right and left-heart-catheterization documenting PA and systemic pressures Documentation of secondary causes of pulmonary hypertension

CT, Computed tomography; BMI, body mass index; MELD, Model for End-Stage Liver Disease; CPR, curved planar reformation; RV, right ventricular; IMA, internal mammary artery; PA, pulmonary artery; TAPSE, tricuspid annular plane systolic excursion. *Variable with respect to age and gender without validated scientific thresholds. †Rudski et al.⁷¹

TABLE 2. Mortality

All-cause mortality
Cardiovascular mortality
Any of the following criteria
Death due to proximate cardiac cause (eg, myocardial infarction, cardiac tamponade, worsening heart failure)
Death caused by noncoronary vascular conditions such as neurological events, pulmonary embolism, ruptured aortic aneurysm, dissecting aneurysm, or other vascular disease
All procedure-related deaths, including those related to a complication of the procedure or treatment for a complication of the procedure
All valve-related deaths including structural or nonstructural valve dysfunction or other valve-related adverse events
Sudden or unwitnessed death
Death of unknown cause
Noncardiovascular mortality
Any death in which the primary cause of death is clearly related to another condition (eg, trauma, cancer, suicide)

TABLE 3. Myocardial infarction

Periprocedural MI (≤ 72 h after the index procedure)

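### Section 4.1.3 does not settle which deaths count towards stopping, and its printed stopping probabilities hold only if the counted death has a 30% rate

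*Combined protocol and SAP*

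**What the plan says.** **The running text of section 4.1.3 limits the rule.** It says "For the purpose of this trial, we will focus on device-related mortality", and it describes the first boundary as met when "two (or more) out of the first three patients died within 6 months on trial due to a device-related death".

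**The rest of the plan does not carry the limit.** The table column reads "When number of 6-month deaths". The reference rate is general: "it is reasonable to assume a 6-month mortality of at least 30% for the high risk patients targeted in this clinical trial". Section 2.3 refers to this section as formal rules on 6-month mortality, without a qualifier.

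**Population.** Looks take place "when 3, 6, and 9 patients have been enrolled and treated with the protocol device". Section 2.3 puts all enrolled patients into the interim analyses, whatever happens to them afterwards.

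**Causality.** Section 7.2 says "Study device causality for SAE's will be graded as unlikely, possible or probably". Section 7.1 and the adverse event form use the same three grades. The UADE form offers five options (not, possibly, probably, definitely, unknown), also for the study device only.

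**Sources of harm.** Section 4.0 lists procedural risks and valve risks, and then adds: "There are risks associated with stenting of the IVC for valve implantation". Section 5.2.1 has the stent placed before the valve. Appendix B, Table 2 includes in cardiovascular mortality "All procedure-related deaths, including those related to a complication of the procedure or treatment for a complication of the procedure", but nothing ties that definition to the stopping rule.

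**The concern.** A stopping rule is usable only if two people given the same deaths reach the same count. Here they need not. A reader of the table counts every death within 6 months. A reader of the text counts only those judged device-related and must decide, without guidance, three things: whether a grade of possible is enough, whether the IVC stent is part of the device, and whether a fatal complication of access or pre-stenting is device-related at all.

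The boundaries are 2 of 3, 3 of 6 and 4 of 9, so the classification of one death can decide a look. Suppose two of the first three patients die, one death graded probably related and the other possible. If possible counts, the boundary of 2 is reached. If it does not, the count is 1 and the trial goes on.

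The table is also what tells a DSMB or IRB how protective the rule is. If the counted event is rarer than the event used in the calculation, the rule stops less often than the table says.

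**Working it through.** **Inputs.** From section 4.1.3: boundaries of at least 2 of 3, 3 of 6, 4 of 9 and 6 of 15; reference mortality 30%; printed probabilities 0.216, 0.105, 0.064, 0.064. The running text names looks at 3, 6 and 9; the table adds 15. Not in the documents: the share *f* of 6-month deaths that would be classed as device-related. I take *f* = 1, 0.75 and 0.50 as assumptions.

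**Step 1: reproduce the table.** Let *p* be the probability that a patient has a counted death, independent between patients. In a block of three patients at *p* = 0.30:

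- P(0) = 0.7³ = 0.343
- P(1) = 3 × 0.3 × 0.7² = 0.441
- P(2) = 3 × 0.3² × 0.7 = 0.189
- P(3) = 0.3³ = 0.027

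The probability of first crossing at each look is then:

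- 3 patients: 0.189 + 0.027 = 0.216.
- 6 patients: (0 so far, then 3) + (1 so far, then 2 or more) = 0.343 × 0.027 + 0.441 × 0.216 = 0.1045.
- 9 patients: after six patients without a stop, P(1 death) = 2 × 0.343 × 0.441 = 0.3025 and P(2 deaths) = 0.343 × 0.189 + 0.441² = 0.2593. First crossing = 0.3025 × 0.027 + 0.2593 × 0.216 = 0.0642.
- 15 patients: the same recursion with six more patients gives 0.0636.

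All four rows match the table. The unconditional probabilities (0.216, 0.256, 0.270, 0.278) do not match after the first row. So the printed figures are stage-by-stage probabilities given no earlier stop, and they add up: 0.216 + 0.1045 + 0.0642 = 0.385 over the looks at 3, 6 and 9, and 0.448 with the row at 15.

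**Step 2: change only the counted event.** If 6-month mortality from any cause is *m* and a share *f* of deaths counts, then *p* = *m* × *f*. For *m* = 0.30 and *f* = 0.50, *p* = 0.15. The first look gives 3 × 0.15² × 0.85 + 0.15³ = 0.0608. The next two give 0.0218 and 0.0099. The sum is 0.0925.

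Cumulative probability of stopping at the looks after 3, 6 and 9 patients:

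| 6-month mortality | All deaths count | Three-quarters count | Half count |
|---|---|---|---|
| 30% | 38.5% | 21.9% | 9.2% |
| 40% | 61.7% | 38.5% | 17.2% |
| 50% | 80.9% | 56.1% | 27.1% |

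With the row at 15 included, the figures are 44.8%, 24.5% and 9.7% at 30% mortality, and 90.3%, 65.9% and 30.9% at 50%.

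**Step 3: look for a definition elsewhere.** Sections 7.1 and 7.2 and the adverse event form give grades but no cut-off. The UADE form has a different scale and no link to the rule. Neither visible form has an item for relation to the procedure or the stent. A clinical events committee appears in the abbreviations and in the DSMB membership conditions of section 4.1.2, but the text does not set one up for this trial or give anyone the task of classifying deaths for the rule.

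**The case against.** The strongest reply is that deaths outside the formal count are not ignored. Under section 7.2 every SAE is reported to the DSMB chair within 24 hours, and the DSMB reviews all SAEs. Section 4.1.2 lets the DSMB meet at any time and recommend termination. Section 2.3 suspends accrual at once if other adverse events, surgical complications among them, are thought excessive. Section 4.1.3 has surgical complications and overall survival monitored at least every six months. All of this stands, and none of it depends on a device-causality grade. But these routes are discretionary and have no threshold, so they do not repair a rule that was meant to supply one.

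A second reply is that a device-related count may be deliberate where background mortality is high. That is a fair design choice, but it needs a definition and probabilities calculated for that event.

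Three stronger readings are tempting, and the documents do not support them:

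- *That procedural, stent or pre-delivery deaths are excluded.* The text does not say so. Being treated with the protocol device fixes when looks happen, and section 2.3 includes all enrolled patients. The matter is unresolved, not decided.
- *That the implanting operator's grade decides whether the trial continues.* No text makes that grade decisive. The adverse event form sends SAEs to a medical reviewer, and the DSMB works to a charter that is not part of these documents.
- *That no form anywhere records relation to the procedure or stent.* Only the adverse event and UADE forms are visible. Section 8.1 refers to CRFs in an addendum, and section 7.2 to an SAE CRF.

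**Conclusion.** The point holds as a contradiction within section 4.1.3, and between it and section 2.3, made worse by an undefined term. The counted death, the causality cut-off, the adjudicator and the population are all open. The printed probabilities are correct arithmetic for an event with a 30% rate, and the plan attaches that rate to mortality in general. If the running text governs and only some deaths are device-related, the rule is weaker than the table states: over three looks, 38.5% falls to 21.9% or 9.2% at 30% mortality, and 80.9% falls to 56.1% or 27.1% at 50%.

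The size rests on assumed shares and on independent deaths with a constant rate. The direction does not depend on the shares: any uncounted death lowers the chance of stopping. A reader might infer that the trial has no protection against procedural deaths. That goes too far, because the gap is in the formal rule and not in safety reporting.

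**What to change.** Reconcile the text and table of section 4.1.3, and section 2.3 with them, in one paragraph:

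1. State one counted event: at least every death within 6 months related to the valve, the IVC stent or the procedure, with possible or undetermined relation counted as related.
2. Count it in every patient in whom the procedure was started, whether or not a valve was delivered.
3. Make the DSMB's classification final for the purpose of the rule.
4. Add items for relation to the procedure and to the IVC stent to the causality field.
5. Restate the table for the event actually counted, with the assumed rate of that event and the cumulative probability beside each stage.

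Using all cardiovascular deaths from Appendix B, Table 2 is possible but debatable: it takes in worsening heart failure, sudden death and death of unknown cause, and so may come close to counting every death.

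The cost in text is one paragraph and two form items. No new committee is needed, since the DSMB already reviews all SAEs. The real cost is that more deaths count and an early stop or pause becomes more likely. At 30% mortality, going from half of deaths counted to all of them raises stopping over three looks from 9.2% to 38.5%, about fourfold (38.5 / 9.2 = 4.2). That is an upper limit for this move, because the proposed event need not include every death. The restated table should show the figure so that the sponsor, DSMB and IRB accept it knowingly.
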